Expected population n	Totally, fifty-seven positive patients diagnosed by PSMA combined with model are enrolled in this clinical trial.
Inclusion criteria	
 1) Male patients with clinically suspected prostate cancer (abnormal digital rectal examination or serum prostate-specific antigen (PSA)); 2) Finish the detection of serum PSA and multi-parameter magnetic resonance imaging (mpMRI); 3) $4 \text{ ng/ml} \leq \text{serum PSA} < 100 \text{ ng/ml}$; 4) Prediction threshold of csPCa evaluated by the model (online system) ≥ 0.60; 5) Finish 18F-PSMA-1007 PET/CT and present positive result; 6) Patients without contraindications of radical prostatectomy.
Exclusion criteria	
 1) Unable to perform PSA test or mpMRI examination; 2) Serum PSA $< 4 \text{ ng/ml}$ or $\geq 100 \text{ ng/ml}$;

	
3) Prediction threshold of csPCa evaluated by the model (online system) <0.60;
 
4) Finish 18F-PSMA-1007 PET/CT but negative result;
 
5) Patients who have negative results in the previous prostate biopsy.
 
6) Patients refuse radical prostatectomy or still choose prostate biopsy.

Exit criteria	
Early withdrawal from the study of the patients can be any of the following, but not limited to the following:
 
1) Patients requiring exit (withdrawal / revocation of informed consent);
 
2) If there are any clinical adverse events or changes in the physical condition of the patients, it is not in the best interests of the patients to continue to participate in the study;
 
3) Patients with poor compliance or unable to truthfully provide relevant information or violate the protocol;
 
4) Patients who died;
 
5) Other reasons for withdrawing from the study (need to be recorded in detail);

Statistical analysis	
Sample size estimation
 
This study is designed for a single group of objective performance criteria. With reference to the opinions of many senior clinical experts and statistical experts, it is considered that the clinically acceptable positive predictive value should not be less than 90%. According to the literature exploration and previous research results, it is expected that the positive predictive value of PSMA combined model is more than 98%. Suppose the significance level is 0.05 (bilateral) and the degree of

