This study is designed for a single group of objective performance criteria. With reference to the opinions of many senior clinical experts and statistical experts, it is considered that the clinically acceptable positive predictive value should not be less than 90%. According to the literature exploration and previous research results, it is expected that the positive predictive value of PSMA combined model is more than 98%. Suppose the significance level is 0.05 (bilateral) and the degree of power is 80%. The required number of positive samples (positive results in PSMA combined model) is 55. Considering the drop rate of 5%, the study is expected to enroll 57 patients.

2). Statistical analysis set

- 1) Full analysis set (FAS): the set of patients determined according to the intention to treat, which refers to the data set of all patients who participated in this study.
- 2) Per protocol set (PPS): refers to the completed trial and excludes patients who seriously violate the scheme (patients violate the selection criteria or exclusion criteria, etc.).
- 3) Security data set (SS): all the patients who participated in this study and conducted at least once safety assessment constitute the security population of this study.

3). Principle of statistical analysis

- 1) IBM SPSS (version 25.0) statistical software is used for statistical analysis.
- 2) All statistical tests use two-sided tests, and a P value of less than 0.05 will be considered to be statistically significant normally.
- 3) Description statistics: the measurement of continuous variables is described by means, standard deviation, and median, interquartile range; categorical variables are described by number and proportion (%).
- 4) The comparison of the two groups of variables will be analyzed by appropriate methods according to the type of variables. T-test or Wilcoxon rank sum test is used to compare measurement indexes between groups. χ^2 test or Fisher exact test is used to compare categorical variables between groups.

4). Group completion status

The selection and completion of the cases are described respectively, and the corresponding statistical analysis of the population is summarized and listed by the enrollment, drop, elimination, completed cases, and the number of cases of each analysis set.

5). Equilibrium analysis of baseline data

Baseline analysis based on full data set (FAS)

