The number of patients enrolled in the group, the number of completions, and the total drop rate are described respectively, and the list of excluded cases and the detailed list of unfinished reasons are listed. The baseline features of the patients are statistically described.

6). Evaluation indexes

The analysis of effectiveness indexes is based on the full analysis set (FAS) and the per-protocol set (PPS) and is described in the table below.

Table 2 Statistical analysis of main indicators ^f

		Results of pathological diagnosis		total
		positive	negative	
PSMA combined model	positive	A	B	A+B
	negative	C	D	C+D
		total	A+C	B+D
				N=A+B+C+D

Positive predictive value (true positive rate)= $A/(A+B) \times 100\%$;

Misdiagnosis rate= $B/(A+B) \times 100\%$.

6.1) Main effectiveness indexes

The most important effectiveness index of this study is the positive predictive value (true positive rate) of PSMA combined model, which is the proportion of the positive results of postoperative pathological diagnosis to all enrolled patients. For the analysis of the primary endpoint, the results of both FAS and PPS will be considered. The positive predictive value of PSMA combined model for csPCa diagnosis and its 95%

CI will be calculated, when the lower limit of 95%CI is greater than the set target value, it is considered that the detection rate of PSMA combined model is up to the standard, which can be used as a proof for a new clinical treatment scheme called biopsy-free radical prostatectomy.

6.2) Secondary effectiveness evaluation index

The secondary endpoint of the study is the detection rate of any-grade PCa (Gleason score $\geq 3+3$) and high grade PCa (hgPCa) (Gleason score $\geq 4+3$) by PSMA combined model, the positive predictive value and misdiagnosis rate of any-grade PCa and hgPCa will be assessed.

Notably, no target value is set for the secondary endpoint indexes, and only the point estimated value and 95% CI are calculated at the time of evaluation.

Safety endpoint analysis

6.3) Safety evaluation

The severity, quantity and incidence of AE, ADR and SAE and their correlation with overall trial, examination or operation and patients are statistically and descriptively analyzed. In addition to the above statistical methods, detailed and additional exploratory analysis may be required and confirmed in the Statistical Analysis Program (SAP).

3、Data management

(1) Raw data verification

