Annex II. Annual implementation plan

December 2022-August 2023: Fifty-seven patients who met the requirement of radical prostatectomy without prostate biopsy are enrolled in the group. The basic personal and clinical information of the patients are recorded in detail.

September 2023-December 2023: We will collate all data, statistical analysis, article writing and contribution.

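### The 5% drop-out allowance is rounded the wrong way: 57 enrolled leave an expected 54 evaluable men, not the required 55 (minor)

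*Combined protocol and SAP*

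**What the plan says.** The sample size paragraph appears twice in the combined protocol and SAP, in the Protocol summary and under Statistical analysis, Sample size. Both give the requirement: "The required number of positive samples (positive results in PSMA combined model) is 55". Both then give the enrolment figure: "Considering the drop rate of 5%, the study is expected to enroll 57 patients".

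The same number recurs in the Protocol summary under Expected population ("Totally, fifty-seven positive patients diagnosed by PSMA combined with model are enrolled in this clinical trial") and in Annex II ("Fifty-seven patients who met the requirement of radical prostatectomy without prostate biopsy are enrolled in the group").

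The target PPV is 90% and the expected PPV is above 98%. Under Main effectiveness indexes, success is declared "when the lower limit of 95%CI is greater than the set target value". The method for that interval is not named. The text available for review neither provides for nor forbids replacing an enrolled man who leaves before surgery. Two short stretches of the protocol, one after section 13 begins and one just before Annex II, were not available, so a rule there cannot be ruled out.

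**The concern.** A drop-out allowance should make the stated loss rate leave the stated evaluable number. Here it does not: 5% of 57 takes the count below 55.

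In most trials one man would not matter. Here the success rule is coarse. Near this sample size the verdict depends on whether zero or one false positive is tolerated, and under some interval methods that changes within a man or two of 55. The size of the evaluable set therefore deserves an exact statement and a rule for protecting it.

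The point concerns the allowance only. Whether 55 is itself the right number for 80% power is a separate question.

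**Working it through.** **Inputs.** From the Sample size paragraph: 55 required, 5% loss, 57 enrolled, target PPV 0.90, expected PPV above 0.98 (0.98 is used below). From Main effectiveness indexes: success if the lower 95% limit exceeds 0.90.

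**1. The plan's figure.** Dividing by the retention rate gives 55/0.95 = 57.89. Multiplying up gives 55 x 1.05 = 57.75. Both round up to 58; 57 is either value rounded down.

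**2. What each enrolment delivers.** 57 x 0.95 = 54.15 and 58 x 0.95 = 55.1. Keeping 55 of 57 allows 2 losses, and 2/57 = 3.5%.

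**3. Chance of keeping at least 55.** Losses are taken as binomial at 5%.
- 57 enrolled, at most 2 losses: 0.0537 + 0.1612 + 0.2376 = 0.452.
- 58 enrolled, at most 3 losses: 1 - 0.330 = 0.670.
- Chance of 53 or fewer evaluable: 0.318 with 57 (4 or more losses), 0.164 with 58 (5 or more losses).

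**4. Lower 95% limit with one false positive, lost men removed from the denominator.**

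| Method | n = 55 | n = 54 | n = 53 |
|---|---|---|---|
| Clopper-Pearson | 0.9028 | 0.9011 | 0.8993 (fail) |
| Wilson | 0.9039 | 0.9023 | 0.9006 |
| Jeffreys | 0.9182 | 0.9167 | 0.9152 |
| Wald | 0.9465 | 0.9455 | 0.9445 |
| Agresti-Coull | 0.8949 (fail) | 0.8931 (fail) | 0.8912 (fail) |

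Wilson fails one man lower, at n = 52 (0.8988).

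**5. Chance of success at a true PPV of 98%, exact limits.** Where one false positive is allowed, it is 0.98^n + n x 0.02 x 0.98^(n-1). Where none is allowed, it is 0.98^n.
- n = 55: 0.3292 + 1.10 x 0.3359 = 0.699.
- n = 54: 0.3359 + 1.08 x 0.3428 = 0.706.
- n = 53: 0.343.

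**6. Averaged over 5% binomial losses, same rule.** Each line weights the mean chance of success with 54 or more evaluable and with 53 or fewer.
- 57 enrolled: 0.682 x 0.698 + 0.318 x 0.348 = 0.587.
- 58 enrolled: 0.836 x 0.694 + 0.164 x 0.347 = 0.637.
- Exactly 55 secured: 0.699.

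**The case against.** The best defence is that this is a one-patient rounding slip with no effect at the expected count. That stands. Under exact limits one false positive passes at both 55 and 54, and the chance of success is 69.9% and 70.6% respectively.

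Four stronger readings are tempting, and the documents do not support them.

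- **Enrolment stops at 57 and nobody may be replaced.** The Sample size paragraph gives 57 as an expected number, and the Expected population entry and Annex II repeat it as the plan. Nothing seen sets a hard stop. The text is silent on replacement.
- **One further loss turns a pass into a fail.** The step from 54 to 53 does this only under Clopper-Pearson, and no interval method is specified. Reaching 53 also takes 4 losses of 57 (7.0%), more than the assumed 5%. It further requires lost men to leave the denominator. That fits the true-positive over all-positive formula, but Main effectiveness indexes also words PPV as a proportion of all enrolled patients. If a lost man stays in and counts as not positive, the picture changes: one loss plus one false positive is 55/57, with a lower limit of 87.89% (exact) or 88.08% (Wilson), and both fail.
- **Men who opt for biopsy are drop-outs from the 57.** Study design and Study content treat them as eligible but not enrolled, and exclusion criterion 6 excludes them. Table 1 does place enrolment in screening, but the Perioperative period list places it later. The losses in question are enrolled men who withdraw consent or exit before surgery.
- **The 45% is wholly the cost of the slip.** Much of it is ordinary binomial variation. With 58 enrolled, the chance of keeping 55 is still only 67%.

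**Conclusion.** The arithmetic point holds without further assumptions: at the plan's own 5%, 57 enrolled are expected to leave 54. The figure is one short of the correctly rounded 58 and covers a loss of 3.5%.

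The effect on the decision is conditional. If exact limits are used, lost men leave the denominator, losses are independent at 5% and the true PPV is 98%, rounding down costs about 5 percentage points of success (64% to 59%). Having no replacement rule as well brings the cost to about 11 points (70% to 59%). Under Wilson limits the cliff lies one man lower. Under Jeffreys or Wald one false positive still passes at 53. Under Agresti-Coull it already fails at 55. Severity is minor.

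**What to change.** Either of two changes is enough.

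1. Restate the allowance: 57 enrolled covers 2 losses (3.5%), and at 5% loss 54 evaluable men are expected.
2. Define the target as 55 men with a read prostatectomy specimen. Replace enrolled men who leave before surgery, list them in the disposition table, and keep them in the FAS, which is defined as all participants. Never replace a man who has been operated on, so that no exchange can depend on pathology.

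The second option protects the count better. Because replaced men remain in the FAS, it does not settle how a man without a specimen enters the FAS estimate of PPV, and the plan should state that alongside the interval method.

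The cost is two or three sentences and, under the second option, a few extra screenings and PET/CT scans. It adds no operations beyond the planned number.

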Before the start of the clinical trial, the person in charge of the trial center trains the researchers participating in the clinical trial, so that the researchers can understand and be familiar with the whole trial process and related operations.

4.4) Standard implementation of including and excluding standards

The patients are screened according to the inclusion and exclusion criteria of the trial scheme to reduce the selective bias.

4.5) Monitoring of clinical trials

Key researchers formulate monitoring plans and appoint independent inspectors to conduct regular on-site monitoring visits to experimental hospitals to ensure that all contents of the research program are strictly observed, and regularly check the database to ensure consistency with the contents of the original materials.

4.6) Blind evaluation

The centralized film reading is blinded, and the image is blinded by the statisticians to prevent the central film reviewers from knowing the subject's disease diagnosis, subject number and other information which can cause bias.

5) . Patients selection criteria

5.1) Inclusion criteria

- 1) Male patients with clinically suspected prostate cancer (abnormal digital rectal examination or serum PSA);
- 2) Finish the detection of serum PSA and multi-parameter magnetic resonance imaging (mpMRI);
- 3) $4 \text{ ng/ml} \leq \text{serum PSA} < 100 \text{ ng/ml}$;
- 4) Prediction threshold of csPCa evaluated by the model (online system) ≥ 0.60 ;
- 5) Finish 18F-PSMA-1007 PET/CT and present positive result;
- 6) Patients without contraindications of radical prostatectomy.

5.2) Exclusion criteria

- 1) Unable to perform PSA test or mpMRI examination;
- 2) Serum PSA $< 4 \text{ ng/ml}$ or $\geq 100 \text{ ng/ml}$;
- 3) Prediction threshold of csPCa evaluated by the model (online system) < 0.60 ;
- 4) Finish 18F-PSMA-1007 PET/CT but negative result;
- 5) Patients who have negative results in the previous prostate biopsy.
- 6) Patients refuse radical prostatectomy or still choose prostate biopsy.

6). Effectiveness evaluation

6.1) Definition

- 1) **True positive:** The diagnosis results of PSMA combined model and pathological examination are both csPCa.

2) False positive: The diagnosis result of PSMA combined with model is csPCa, while the pathological examination is not.

6.2) Main effectiveness index

Positive predictive value

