Definition: The patients with positive results of PSMA combined model and pathological examination accounted for the proportion of all patients with positive results of PSMA combined model.

Calculation method: Positive predictive value= $\frac{\text{true positive}}{\text{true positive}+\text{false positive}} \times 100\%$

6.3) Secondary effectiveness index

1) Misdiagnosis rate

Definition: The patients with positive results of PSMA combined model and negative results of pathological examination accounted for all patients with positive results of PSMA combined model.

Calculation method: Misdiagnosis rate= $\frac{\text{false positive}}{\text{true negative}+\text{false positive}} \times 100\%$

7. Safety evaluation

The severity, quantity and incidence of AE, ADR, and SAE and their correlation with overall trial, examination or operation and individual patients are statistically and descriptively analyzed.

(2) Study flow

1). Study flow chart

[figure not shown]

Table 1 The schedule of the screening period, perioperative period, and evaluation period for this trial.

Items	Screening period (-7~0 days)	Perioperative period of radical prostatectomy (1- 14 days)	Evaluation period
Demographic data	▲		
Signs and symptoms	▲		
Completed the blood test ^a and mpMRI examination	▲		
Evaluation by the online diagnostic model	▲		
Signing of informed consent forms	▲		
¹⁸ F-PSMA-1007 PET/CT examination ^b	▲		
Enrollment	▲		
Radical prostatectomy ^c		▲	

Reading of pathological slices			▲
Follow up and adverse events	▲	▲	▲

^a Prostate cancer marker test (Serum total PSA).

^b The researchers decide whether an ¹⁸F-PSMA-1007 PET/CT examination is performed based on the results of the risk probability by online diagnostic model evaluation.

^c The researchers decide whether the radical prostatectomy is performed based on the decisions of the patients and their relatives. Full preoperative communication is needed.

mpMRI, multi-parameter magnetic resonance imaging; ¹⁸F-PSMA-1007 PET/CT, ¹⁸F-prostate-specific membrane antigen-1007 positron emission tomography/computed tomography; PSA, prostate specific antigen.

2). Screening period (-7~0 day)

The following process will be completed during the screening period:

- Allocation of patient's number;
- Collection of demographic information (age, place of origin, height, weight, and healthy condition, etc.);

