Clinical research will follow the relevant provisions of the Helsinki Declaration of the World Medical Congress. Prior to the commencement of the study, the study shall be approved by the Ethics Committee before it can be implemented. Before each subject enrolls in this study, the researcher has the responsibility to fully and comprehensively introduce the purpose, procedure, and possible risks of the study to the subject or his agent, and to sign a written informed consent form. The patients should know that they have the right to withdraw from the study at any time, and the informed consent should be kept as a clinical research document for reference. In the course of the study, the patient's personal privacy and data confidentiality will be protected.

(2) Examination and approval of the trial scheme

The approval of the clinical trial program is carried out by the ethics committee, and the clinical trial can only be carried out after the final ethical approval has been obtained.

(3) Informed consent process and informed consent form text

Before being enrolled in this study, the researcher must explain the details of the clinical trial to the subject or his guardian, including the trial content, trial purpose, expected efficacy, possible adverse events, and countermeasures. Only after the patients fully understand the experiment and sign the informed consent form can they be selected.

Incapacitated patients can also enter clinical trials if the ethics committee agrees in principle and the researchers believe that it is in their own interest to participate in clinical trials, but their guardians should sign and date them before the trial. Patients

with acute ischemic stroke may not be in a coma clinically, but their cognitive ability and hand function are affected. Such patients should be signed and dated by their guardians before the trial.

When the subject or his guardian is unable to read, there shall be a witness present in the informed process. After a detailed explanation of the informed consent form, the witness reading the informed consent form is consistent with the oral informed content. With the oral consent of the subject or his guardian, the witness shall sign and date the informed consent form, and the signature of the witness shall be on the same day as that of the researcher.

8、Deviation of the clinical trial scheme and provisions for revision of the clinical trial scheme

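### Section 7 (3) requires patients to understand and sign before selection, then allows guardian-signed entry of incapacitated and acute ischemic stroke patients, and no eligibility criterion addresses capacity

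*Combined protocol and SAP*

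**What the plan says.** Section 7 (3), on the consent process, makes selection conditional on the patient's own understanding and signature: "Only after the patients fully understand the experiment and sign the informed consent form can they be selected".

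The next paragraph opens a second route: "Incapacitated patients can also enter clinical trials if the ethics committee agrees in principle". A further condition is that the researchers believe participation to be in the patient's interest. For these men, "their guardians should sign and date them before the trial".

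The same paragraph then turns to patients "with acute ischemic stroke may not be in a coma clinically, but their cognitive ability and hand function are affected", and continues: "Such patients should be signed and dated by their guardians before the trial".

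Section 7 (1) names the subject or his agent as the person to be informed. Section 7 (3) names the subject or his guardian, both for the explanation and for the witness procedure.

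On the decision to operate, the summary and section 2 (1) 2) refer to patients and their families. Footnote c of Table 1 says: "The researchers decide whether the radical prostatectomy is performed based on the decisions of the patients and their relatives", and adds that full communication before surgery is needed. Exclusion criterion 6 removes men as follows: "Patients refuse radical prostatectomy or still choose prostate biopsy".

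**The concern.** The consent section gives two answers to the question of who must understand and sign. One of them concerns a patient group that has nothing to do with this trial.

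The consequence is unusual for a diagnostic study, because a positive test leads straight to removal of the prostate without histology. The Background describes false-positive harm as something that cannot be undone. The Risk subsection before the reference list names removal of a tumour-free prostate as the main risk. A man who cannot weigh that risk against the usual biopsy could be entered on someone else's signature. He does not need the trial to obtain a diagnosis, because the biopsy pathway remains open to eligible men who do not enrol.

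**Working it through.** No figure in the plan depends on this point, so there is nothing to recompute. The check sets the relevant texts side by side.

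1. **Entry rule against entry rule, both in section 7 (3).** The first requires that the patient fully understands and signs. The second admits patients who lack capacity, with a guardian signing. A man without capacity cannot satisfy the first. The text does not say that the second overrides it, or how the two fit together.

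2. **Conditions on the guardian route.** For incapacitated patients there are two: agreement in principle by the ethics committee, and the researchers' view that entry is in the patient's interest. The stroke sentences state no conditions of their own, and it is unclear whether they inherit these two.

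3. **Relevance of the stroke text.** Stroke is not in the study purpose, the six inclusion criteria, the six exclusion criteria or the procedures. It otherwise appears only among the postoperative complications in section 5 (2) (grade IVa, with cerebrovascular death under grade V). The wording may have been carried over from another protocol. Section 8 similarly describes multi-center consultation in a single-center study. The documents do not state this origin, so it remains an inference.

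4. **Consent text against the decision text.** The summary, section 2 (1) 2) and Table 1 footnote c each describe a decision by the patient and his family or relatives. None describes the family deciding in place of the patient. The guardian clause allows that substitution.

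5. **Does an eligibility criterion close the gap?** The criteria are printed twice, in the summary and in 5.1) and 5.2), and neither list mentions capacity. Inclusion criterion 6 requires no contraindication to radical prostatectomy, but contraindications are not defined. It might stop a man with an acute stroke. It would not stop a surgically fit man without capacity.

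6. **Do the two conditions close it?** Agreement in principle does not amount to review of the individual case. The test of the patient's interest is largely answered in advance by the Risk/benefit assessment, which concludes that benefit exceeds risk and argues that even men with non-malignant pathology gain. On that reasoning the test would exclude few men.

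**The case against.** The strongest reply is that the incapacity clause is a conditional exception to the patient-signature rule. Its wording adds to the rule, and it carries two safeguards. The study also commits to the Helsinki Declaration, and a man in an acute stroke is unlikely to be judged fit for prostatectomy. All of this is fair. It makes flat contradiction too strong a description of the incapacity clause, and it suggests that practical exposure is very small. It does not explain the stroke sentences, supply a capacity criterion, or say how the two rules fit together.

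A reader might infer more than the documents support, in three ways.

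- **That the protocol requires the patient alone to choose surgery.** It does not. Every statement of the decision pairs him with family or relatives, and section 7 provides for an agent or guardian to be informed. Exclusion criterion 6 refers to the patient's refusal or choice but does not rule out a proxy.
- **That 2% to 10% of these men would be harmed.** Those figures are 1 − 0.98 = 0.02 and 1 − 0.90 = 0.10, the complements of the expected and target positive predictive values. They apply to every enrolled man, whoever signs, so they do not measure this flaw. The 90% is a success target, so the true value could be lower. The complement also counts men with Gleason 3+3 cancer, whereas the stated main risk is a prostate with no tumour.
- **That guardian entry changes the population to which the result applies.** The objective is the predictive value and the feasibility of biopsy-free surgery. It does not define a population of men who decide for themselves, and nothing suggests that the number affected would move the estimate.

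It can also be said that barring proxy consent is an ethics-policy choice which the documents do not compel. That stands. What they compel is reconciliation; removing the clause is the simplest way to achieve it.

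**Conclusion.** The point holds as an internal inconsistency in section 7 (3), together with an entry rule for a patient group unrelated to the trial and no capacity criterion to limit either. It is a patient-protection matter and should be corrected. Few men, if any, would be affected, but the exposure is irreversible surgery without histology while biopsy remains available. There is no effect on sample size, alpha, power or the primary analysis.

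The conclusion rests on the protocol text alone. The consent form's own wording was not available, nor were some stretches of text near sections 13 and 14 and before Annex II. A stricter rule in the consent form would reduce the risk in practice, but the protocol text would still need correcting.

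**What to change.** 1. Delete the two acute ischemic stroke sentences from section 7 (3).
2. Reconcile the incapacity clause with the understand-and-sign rule. The simplest way is to remove the clause and add an inclusion criterion to 5.1), repeated in the summary, that the patient has capacity to consent and signs for himself. If the sponsor wishes to keep a guardian route, the protocol should state it as an explicit exception, justify it for biopsy-free surgery, and say how it fits with exclusion criterion 6.
3. Align the agent wording in section 7 (1) and the guardian wording in section 7 (3), including the witness paragraph, with whichever rule is adopted.
4. Keep the witness procedure for men who have capacity but cannot read.

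The cost is a wording amendment with ethics committee approval and a matching check of the consent form. With the simplest option, a negligible number of otherwise eligible men could not enter. No statistical section changes.
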